## **B.** Specific Aims

Primary:

- 1. To estimate the proportion of additional infectious etiologies of febrile illness among patients presenting with an undifferentiated fever of 3 to 21 days duration.
- 2. To compare the use of antimicrobials in patients with undifferentiated fever in whom additional microbiological tests have been performed versus patients with clinical diagnosis alone.

Secondary:

- 3. To evaluate the appropriateness of the empiric antibiotic therapy based on clinical diagnosis alone and after laboratory confirmation.
- 4. To estimate the correlation between clinical diagnosis with laboratory diagnosis in patients with undifferentiated fever.
- 5. To compare the outcome among patients whose treatment is based on microbiological diagnosis compared to the patients whose treatment is based on clinical diagnosis alone.

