#### c. Inclusion criteria

- 1. Age 16 years or older
- 2. Documented fever (T ≥100.4F or ≥38C) of 3 days to 21 days duration
- No obvious diagnosis found on the basis of clinical, radiological, or initial routine laboratory tests\*
- 4. Admitted to the medical unit of hospital
- 5. Signed ICF (informed consent form)

(\* Initial routine laboratory tests for an etiologic diagnosis of febrile illness work up includeblood and urine cultures, malaria RDT or thick and thin smears, sputum culture and GeneXpert for MTB (if suspected on chest X-ray), and serologies for scrub typhus, dengue, Dengue, Scrub typhus, Leptospirosis, Brucellosis, Kala azar, and HIV, as indicated based on clinical picture)

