## Additional Evaluations for the Study

For patients without an obvious cause of fever and an inconclusive work up after standard of care evaluations, additional serological tests as a part of undifferentiated febrile illness work up will be performed, including:

- a. Clinical evaluation: includes thorough history and physical examinations based on a standard questionnaire and data collection tool
- b. Additional Microbiological Evaluations: If above listed laboratory and microbiological tests do not indicate a conclusive diagnosis, the patient's blood will be processed for additional Serological tests as a part of undifferentiated febrile illness work up. These tests will help to establish diagnosis of the following infections:
  - Murine typhus
  - Bartonellosis
  - Q-fever
  - Chikungunya
  - 7ika
  - Japanese B encephalitis
  - West Nile virus
- 5. Use of antimicrobials in the patients with and without an etiological diagnosis and their outcome at the time of discharge from the hospital will be recorded.
- g. Laboratory Methods

For the purpose of the study, following samples will be collected from 50% of randomly assigned patients for additional microbiological testing.

- 1. Blood cultures, 2 sets from 2 different sites from all study patients (20 mL total)
- 2. Serum samples for serological testing (4 mL)

After obtaining appropriate consent, total 25 mL blood will be collected from each patient assigned to the additional testing arm. Blood samples will be cultured in liquid media and held in the incubator for 7-days.

Urine will be taken to the lab for routine examination and culture will be performed only if there are >10 pus cells or patient reports urinary symptoms.

Gram stain, AFB stain and Genexpert will be performed on sputum samples.

As a part of routine febrile illness work up, the serum samples will be tested for HIV, scrub typhus, dengue, leptospirosis, brucella, malaria, and kala azar.

Additional serum sample will be processed for further serological testing for Chikungunya, Zika, *Coxiella burnetii* (Q-fever), *Bartonella henselae* (Bartonellosis), *Rickettsia typhi* (murine typhus), Japanese B encephalitis, and West Nile virus using ELISA and/or Rapid Diagnostic Test (RDT), as applicable. Although molecular tests have a higher sensitivity and specificity, molecular testing has not been planned for this study because of the budget limits.

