#### i. Follow up and Expected Outcomes

During the hospital stay, patients will be followed up for new laboratory results, changes in treatment plan and outcomes. The patient outcomes will be recorded as:

- a. time to defervescence;
- b. de-escalation or readjustment in antimicrobials;
- c. complete recovery and discharge vs. partial recovery and discharge vs. death.

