## j. Data Collection, Data Analysis and Sample Size

Demographic, clinical, radiological, and laboratory data will be collected and entered into a password protected database. To minimize the errors, data will be directly entered into the database using REDCap Database questionnaires.

Data analysis will include the followings:

- 1. Demographics and baseline characteristics of patients will be analyzed and compared between the two groups.
- 2. Clinical diagnosis and laboratory confirmation of diagnosis will be used to estimate the proportions of various infectious etiologies of febrile illness in patients presenting with a febrile illness of 3-21 days duration. (Specific aim-1)
- 3. Number, type, dose and duration of antimicrobials used to treat the patients will be collected and compared between the two groups: clinical diagnosis alone versus clinical plus microbiological diagnosis. (Specific aim 2)
- 4. Appropriateness of the empiric antibiotic therapy will be determined by an independent physician expert after the laboratory confirmation of the diagnosis. Comparison between the two groups (clinical diagnosis vs. microbiological diagnosis) will be done by calculating the proportion of cases who received appropriate antibiotics divided by the total number of cases for whom empiric antibiotics were administered. (Specific aim-3)

- 5. Pretest probability for clinical diagnosis and posttest probability after laboratory-based diagnosis will be calculated and correlated for bacterial, rickettsial, viral infections versus other causes of fever. (Specific aim-4)
- 6. Clinical outcomes will be compared for patients whose treatment is based on clinical diagnosis alone (Group 1) versus the patients whose treatment is based on clinical plus microbiological diagnosis (Group 2). Composite Positive outcome (complete or partial recovery) and Negative outcome (in-hospital death) will be compared between the two groups. (Specific aim-5)

Demographics and baseline characteristics of patients will be expressed in percentages, means±SD, 95% confidence intervals, and/or median±IQR, as appropriate. Proportions will be compared between the two groups with Chi-square tests. Numerical variables will be expressed as Means/SD/95% confidence intervals and Median/IQRs, whereas Student T test or Mann-Whitney test, respectively, will be used for statistical comparisons. Alpha will be set at 95% (level of significance, p <0.05).

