## APPENDIX – 1.

# **DEFINe Study Questionnaire for Database**

## **Screening Questions**

## A. Definition of Acute Undifferentiated Fever (AUF)

Acute undifferentiated fever (AUF) will be defined as a febrile illness with a temperature of 38°C (100.4°F) or higher for at least a duration of 3 days to 21 days, which presents without an obvious cause on the basis of clinical, radiological, and rapidly available laboratory investigations, and not associated with nosocomial infection, neutropenia, or immunosuppressing conditions [10].

No.	Question	Yes	No
a1	Temperature 38C (100.4F) or higher?		
a2	Duration of fever > 3 days and <21 days?		
a3	Cause of fever unknown after routine work up including		
	clinical, radiology and lab evaluations?		
a4	Is it a Nosocomial infection?		
a5	Neutropenia ruled out?		
a6	Immunosuppression present?		
a7	Does the patient meet all criteria for undifferentiated fever?		
	(Needs to answer "Yes" to 1,2&3, and "No" to 4,5,&6)		

If answer to a7 is "Yes", proceed with questions in "b. Inclusion/Exclusion criteria"

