# C. Clinical and Laboratory Questionnaire (Standard of Care Evaluation for all participants)

No.	Questions/ Variables	Data / value	Unit
	BASELINE CLINICAL DATA		
C1	Duration of fever	No. of days	
C2	Clinical Diagnosis		
C3	System involvement	RTI, GI, UTI, CVS, CNS,	
		SSTI, Blood, Sepsis,	
		Lymphatic, Other	
C4	Comorbidities	None, DM, HTN,	
		COPD/chronic	
		pulmonary dis., CHF,	
		MI, PVD, CLD/Liver	
		failure, PUD, CVA,	
		hemiplegia, dementia,	
		CTD, AIDS, solid	
		tumor, lymphoma,	
		leukemia, other	
C5	Temperature in Celsius (baseline at		Celcius
	presentation)		
C6	BP (baseline at presentation)		mmHg
C7	Pulse (baseline at presentation)		per min.
C8	Resp rate (baseline at presentation)		per min.
C9	SaO2 (baseline at presentation)		%
C10	WBC (baseline at presentation)		per cumm
C11	ANC (baseline at presentation)		per cumm
C12	ALC (baseline at presentation)		per cumm
C13	AEC (baseline at presentation)		per cumm
C14	Hgb (baseline at presentation)		g/dL
C15	Plt		per cumm
C16	CRP		
C17	ESR		per hour
C18	Cr		
C19	ALT		
C20	AST		
C21	UA: pus cells		
	MICROBIOLOGICAL DATA		
M1	Blood culture result	Organism name	
M2	Urine culture result	Organism name	
M3	Sputum culture result	Organism name	
M4	Pus culture	Organism name	
M5	GeneXpert	Positive/negative	
M6	Dengue serology	NS1, IgM, IgG	
M7	Scrub typhus	Positive/negative	

M8	Malaria RDT	P falciparum, P vivax,
		other
M9	Kala Azar	Positive/negative
M10	Brucella	Positive/negative
M11	MTB	Positive/negative
M12	Leptospirosis	Positive/negative
M13	Hepatitis A	IgM
M14	Hepatitis E	IgM
M15	Hepatitis B	HBsAg
M16	Hepatitis C	HBC Ab
M17	HIV	
M18	Other test results ()	
M19	Other test results ()	
M20	Other test results ()	
	RADIOLOGICAL DATA	
R1	X-ray finding	Consolidation,
		Infiltrates, Pleural
		effusion, CHF, ARDS,
		other
R2	CT Chest	Consolidation,
		Infiltrates, Pleural
		effusion, CHF, ARDS,
		other
R3	CT Abdomen	Hepatomegaly,
		pancreatitis,
		Cholecystitis, Gall
		stone, Ascites,
		appendicitis, typhlitis,
		intrabdominal
		abscess,
		lymphadenopathy,
		other
R4	USG Abdomen	Hepatomegaly,
		pancreatitis,
		Cholecystitis, Gall
		stone, Ascites,
		appendicitis, typhlitis, intrabdominal
		abscess,
		lymphadenopathy, other
R5	CT/MPI ckull	
KO	CT/MRI skull	Abscess, Meningitis,
		Encephalitis,
		parameningeal focus, other
		otilei

R6	Echocardiogram	Valvular vegetation,
		Pericardial effusion,
		other
	ADDITIONAL SEROLOGICAL EVALUATIONS	Results
	(for Group B patients only)	
D1	Murine typhus	Positive, negative, NA

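### Aim 3 compares the arms on antibiotic appropriateness judged after laboratory confirmation, but the seven added serologies exist only in Group B, and the protocol does not settle which therapy is rated

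*Protocol*

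**What the plan says.** Aim 3 (section 4.B, secondary) is worded "To evaluate the appropriateness of the empiric antibiotic therapy based on clinical diagnosis alone and after laboratory confirmation". Section 5.j, item 4, sets the rating: "Appropriateness of the empiric antibiotic therapy will be determined by an independent physician expert after the laboratory confirmation of the diagnosis". The two groups are then compared on "the proportion of cases who received appropriate antibiotics divided by the total number of cases for whom empiric antibiotics were administered".

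The added serologies belong to one arm. Section 5.g states that "following samples will be collected from 50% of randomly assigned patients for additional microbiological testing", and Appendix 1, part C, heads the seven results "for Group B patients only". Both arms enter under the inclusion criterion "No obvious diagnosis found on the basis of clinical, radiological, or initial routine laboratory tests" (section 5.c). Screening item a3 in Appendix 1 asks the same thing ("Cause of fever unknown after routine work up including").

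The therapy to be rated is described in different ways. Section 4.B and section 5.j, item 4, speak of empiric therapy. The later paragraph of section 5.j on aims 2 and 3 speaks of antibiotic use in general. Field AM6 in Appendix 1, part E, takes one rating per patient for the antimicrobials used. The sample size section plans for a rise from 70% to 90%.

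**The concern.** The intervention is extra test results, and those results also form part of the yardstick for this outcome. A Group B regimen may be judged against a serological diagnosis that nobody could have had for a matching Group A patient. Randomisation does not remove this, because the difference in information arises after allocation. An arm difference in rated appropriateness then mixes a change in prescribing with a change in what the rater can see.

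The unsettled object of rating adds to this. If the regimen started before the added results is rated, those results cannot have changed it. If all therapy is rated, the empiric wording and the denominator in item 4 do not fit. Aim 3 as worded in section 4.B can also be read as a before/after rating, which the single AM6 field cannot supply.

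At stake is whether the aim 3 result can be read as an effect of testing.

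**Working it through.** **1. The plan's own figure.** For 70% v 90%, two-sided 5% and 80% power, with unpooled variance: n = (1.960 + 0.842)² × (0.7×0.3 + 0.9×0.1) / 0.2² = 58.9, so 59. This agrees with the protocol, read as per arm. The same formula gives its 97, 91 and 79. The arithmetic is not in question; the issue is what the two percentages measure.

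**2. Can identical prescribing give different ratings?** Inputs from the sample size section:
- 97 per arm;
- a cause identified in 30% v 50%, applied here to Groups A and B;
- 70% as Group A's overall share rated appropriate.

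Let k and u be the shares rated appropriate with and without a known cause. The documents give neither, so u is assumed and varied. Prescribing is the same in both arms, and k is taken as the same for causes found by routine and by added tests.

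- Group A: 0.3k + 0.7u = 0.70, so k = (0.70 − 0.7u)/0.3
- Group B: 0.5k + 0.5u
- B − A = 0.2(k − u)

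Exact rejection probability, uncorrected chi-square, two-sided 5%:

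| u | k | Group B | B − A (points) | 97 per arm | 117 per arm |
|---|---|---|---|---|---|
| 80% | 46.7% | 63.3% | −6.7 | 16.9% | 19.0% |
| 75% | 58.3% | 66.7% | −3.3 | 8.1% | 8.5% |
| 70% | 70.0% | 70.0% | 0 | 5.1% | 5.0% |
| 65% | 81.7% | 73.3% | +3.3 | 8.2% | 8.7% |
| 60% | 93.3% | 76.7% | +6.7 | 18.4% | 21.0% |

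The difference vanishes only when knowing the cause does not alter the rating (k = u). The sign is open: a viral result can make an antibiotic look inappropriate, and a rickettsial result can support one.

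Holding k at 70% and letting Group A vary gives smaller effects at 97 per arm. For u = 90%, 84% v 80% (11.3% rejection); for u = 50%, 56% v 60% (8.7%).

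**3. Would one common-information rating repair the arm comparison?** Suppose the rater is masked to arm and sees only what both arms have. With identical prescribing, the arms agree and rejection is 5%. Now let 20% of Group B regimens change because of the added results (50% − 30%, assumed), and let the rater, without those results, score them at r instead of 70%. Group B reads 0.8×0.70 + 0.2r:
- r = 50%: 66%, rejection 9.4% at 97 per arm;
- r = 90%: 74%, rejection 9.6%.

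A true 70% v 90% would be detected with about 95% probability at 97 per arm. Used alone, this rating could miss the effect that aim 3 is meant to show.

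**4. Can the form support a rating at a fixed time?** Appendix 1, part E, records route, dose per day and number of days, without start or stop dates. Part F records discharge status or death and the composite. It has no field for the outcome "de-escalation or readjustment in antimicrobials" named in section 5.i.

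**The case against.** Several objections have force.

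- **Group A is not without a reference.** A reader might infer from the entry criterion that Group A has no laboratory diagnosis to be rated against. The documents do not support that. Section 5.g lists blood cultures from all study patients, held for 7 days, and routine serologies remain. The calculation above itself gives 30% of Group A a known cause.
- **No direction or size is established.** A reader might infer that the plan favours testing. The illustration runs from no difference to 6.7 points either way and rests on an assumed u.
- **Hiding the added results from the rater would defeat the aim.** This stands, as step 3 shows. Such a rating cannot be the sole answer to aim 3.
- **Some of the conflict is loose wording, and rating time and masking are often left to an SAP.** The general reference to antibiotic use may be shorthand for item 4. But item 4 itself fixes both an arm comparison and a post-confirmation rating, and one AM6 field cannot hold two ratings. A later document would have to change these, not just fill them in.
- **Aim 5.** Section 5.j says only that adjustment for type of infection will be considered, and system involvement is recorded at baseline. The objection therefore reaches only a type of infection learned from results after randomisation. The unadjusted comparison is not affected.

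**Conclusion.** The point holds for aim 3 as written. The protocol compares arms on a rating whose reference information differs by arm, so a difference in either direction can appear with identical prescribing. With 97 per arm the illustration gives 0 to 6.7 points and 5% to 18% rejection. This assumes 30% v 50% identification, 70% appropriate in Group A, and u between 60% and 80%. These figures show what can happen; they do not estimate the bias.

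Separately, the passages do not agree on the therapy rated, and the planned 70% to 90% cannot be an arm effect on therapy given before the added results.

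A reader might infer that the trial's main conclusions are compromised. They are not: aim 3 is secondary and the primary aims do not use this rating. The matter should be fixed before ratings begin.

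**What to change.** 1. Use one wording for the rated regimen in section 4.B, both places in section 5.j, the sample size section and Appendix 1, part E. Record two ratings: the empiric regimen before the added results, and the regimen at one fixed later time. Add start and stop dates for AM1 to AM5.
2. Take the before/after contrast, as section 4.B words it, within Group B, judging both regimens against the same final diagnosis. Call it descriptive, because therapy also changes over time without the added tests.
3. Compare the arms on the later regimen as a secondary check, with the rater masked to arm and using only information common to both. State that this does not credit changes made because of the added results. If the item 4 rating is also compared by arm, state that the difference mixes prescribing with available information and is not an effect of testing.
4. Add a form field for the de-escalation or readjustment outcome of section 5.i.
5. Minor, aim 5: do not adjust for a type of infection learned after randomisation. Use baseline factors only (qSOFA, updated Charlson, and baseline system involvement if wanted).

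The cost is wording, several form fields, and a second rating by the physician already planned. Testing Group A serum is not required; it would add 97 × 7 × Rs 500 = Rs 339,500 to a budget of Rs 405,900.

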#### Sample size determination and assumptions:

For specific aim 1, a reduction of antimicrobial use in about 15% patients is expected after additional laboratory confirmation of the diagnosis including viral infections. Assuming this decrease in antibiotics from 90% to 75%, 95% confidence interval, and 80% power, required sample size would be 97 in each arm. With similar assumptions for specific aim 3, an improvement in antimicrobial therapy from 70% to 90% would require 59 patients.

For specific aim 2, assuming an improvement in identification of causative agents from 30% to 50%, 95% confidence interval, and 80% power, required sample size would be 91.

For specific aim 5, an improvement in clinical outcome for patients whose treatment is based on microbiological diagnosis by 20%, from 60% to 80%, 95% confidence interval, and 80% power, the required sample size would be 79 in each arm.

Based on above calculations, minimum sample size needed would be 97 in each arm. Including a 20% loss for failure to consent and loss to follow up, total sample size needed will be 117 in each arm.

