# F. Outcomes

Outcome variable	Results
Outcome at the end of hospitalization	Discharge- complete recovery,
	Discharge- partial recovery,
	Death
Composite outcome at the end of	Good Outcome (complete plus
hospitalization	partial recovery)
	Poor outcome (Death)

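### The aim 5 outcome scale has no value for leaving hospital alive without recovery, so such a patient must be entered as a positive outcome or left blank

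*Protocol*

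**What the plan says.** Protocol section 5.i limits observation to the admission: "During the hospital stay, patients will be followed up for new laboratory results, changes in treatment plan and outcomes". The final status is then recorded as "complete recovery and discharge vs. partial recovery and discharge vs. death", next to time to defervescence and changes in antimicrobials.

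Section 5.j, item 6, builds the aim 5 endpoint from that status: "Composite Positive outcome (complete or partial recovery) and Negative outcome (in-hospital death) will be compared between the two groups". The text that follows adds a Cox model for aim 5 but does not name its event.

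Appendix 1, part F, carries the same scale into the database. The only options for a patient who leaves alive are complete recovery and "Discharge- partial recovery". The composite field pools these two as good and has "Poor outcome (Death" as its only unfavourable value. There is no residual option, although the comorbidity and imaging fields of the same questionnaire have one.

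The sample size text plans aim 5 on an improvement "from 60% to 80%, 95% confidence interval, and 80% power, the required sample size would be 79 in each arm" and sets the final size "Including a 20% loss for failure to consent and loss to follow up". Section 6 lets patients withdraw consent at any time. Section 4.B lists aim 5 as secondary.

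**The concern.** An inpatient fever study can expect some patients to go home no better, to be moved to another hospital, or to leave against advice. These patients are neither dead nor recovered. Because any outcome recorded for a patient who leaves alive is positive by construction, the composite measures leaving hospital alive rather than recovery.

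This cannot be left to a later analysis plan. Such a plan can decide how to analyse recorded categories, but it cannot recover a disposition that the form never collected. The composite is also already fixed in the Protocol and on the form.

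What is at stake is the aim 5 comparison. With death as the only unfavourable event, a few exits without recovery could matter as much as the deaths. The Cox model is exposed in either direction. If its event is recovery, an early exit entered as partial recovery counts as a fast success. If its event is death, the same exit is censored for a reason that may be related to prognosis.

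**Working it through.** **1. Where each way of ending the stay can be recorded**

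| End of stay | Option in 5.i and Appendix 1, part F | Class in 5.j item 6 |
|---|---|---|
| Discharged, fully recovered | complete recovery | positive |
| Discharged, partly recovered | partial recovery | positive |
| Died in hospital | death | negative |
| Discharged, not improved | none | positive if entered as partial recovery, otherwise missing |
| Transferred to another hospital | none | the same |
| Left against advice | none | the same |

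The three places in the Protocol agree with one another, so this is a gap in the scale and not a contradiction.

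**2. The plan's own figure for aim 5**

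Inputs: 60% and 80%, 80% power (sample size text); significance level from section 5.j, "Alpha will be set at 95% (level of significance, p <0.05", read as two-sided 0.05 because sidedness is not stated.

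n = [p1(1−p1) + p2(1−p2)] × (1.960 + 0.842)² / (p1−p2)²
= (0.24 + 0.16) × 7.849 / 0.04 = 78.49, rounded up to 79 per arm.

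The stated 79 reproduces. The problem is the definition, not the arithmetic.

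**3. What 60% and 80% mean on this composite**

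As defined, negative = 1 − positive = in-hospital death. If the planning rates refer to this composite, mortality is 1 − 0.60 = 40% in Group 1 and 1 − 0.80 = 20% in Group 2. With 117 per arm that is 117 × 0.40 ≈ 47 and 117 × 0.20 ≈ 23 deaths. A 20-point gain is impossible on a death-only scale unless Group 1 mortality is at least 20%. This suggests that poor outcome meant more than death when the study was sized, but the Protocol does not say so.

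**4. How far the coding can move the comparison**

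One patient is 1/117 = 0.85 percentage points of an arm's positive rate. Beyond that, rates must be assumed, because the Protocol gives none for death or for live exits without recovery. Two illustrations with 117 per arm, Group 1 v Group 2:

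| Assumed rates | Exits counted as | Positive rate | Power |
|---|---|---|---|
| Death 5% v 2.5%, exits 10% v 5% | positive | 95.0% v 97.5% | 0.17 |
| | not positive | 85.0% v 92.5% | 0.44 |
| | excluded | 94.4% v 97.4% | 0.20 |
| Death 5% v 2.5%, exits 5% v 5% | positive | 95.0% v 97.5% | 0.17 |
| | not positive | 90.0% v 92.5% | 0.10 |
| | excluded | 94.7% v 97.4% | 0.18 |

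Example of the excluded row: (1 − 0.05 − 0.10)/(1 − 0.10) = 0.85/0.90 = 94.4%. Power in the excluded rows was computed at the full 117 and is therefore slightly too high.

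In the first illustration the coding changes the difference from 2.5 to 7.5 points. In the second the difference stays at 2.5 points, and counting the exits as not positive lowers power. The effect depends on rates that the documents do not supply.

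**The case against.** A reader might infer that the plan counts patients who transfer or leave against advice as successes, and that this hides harm. The documents do not say that. Positive is defined as complete or partial recovery, which an unimproved patient does not meet, and staff could leave the field empty and treat the patient as lost. That objection stands. What remains is that the form allows only those two entries and that both are unsatisfactory.

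A reader might also infer that such exits differ between arms because the trial is open-label. Nothing in the Protocol indicates this. Nor does the 20% allowance show how many exits are expected: the difference between 117 and 97, 20 per arm, pools failure to consent with loss to follow-up and gives no split.

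Three further points are fair. Withdrawal of consent is a study status, and its absence from a clinical outcome scale is not an error. Aim 5 is secondary, and the primary aims on etiology and antimicrobial use do not depend on this field. The form keeps the three-level status and section 5.i also records time to defervescence, so the composite is not the only outcome information. These points limit the reach of the problem. They do not remove it, because the three-level status has the same gap.

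**Conclusion.** The point holds in a limited form. The end-of-stay scale has no value for a live exit without recovery. Such a patient is either recorded as a positive outcome or drops out of the aim 5 comparison, and either can bias it.

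The size and direction cannot be estimated from the documents. The figures in step 4 are illustrations on assumed rates and do not show that an unfavourable rate would be halved or a difference between arms concealed.

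The firmest sign in the document that the composite is too narrow is its own planning rates: 60% and 80% positive would mean 40% and 20% in-hospital mortality. That inference is conditional on those rates referring to this composite, which the Protocol does not state.

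The change should be made, but it concerns a secondary aim.

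**What to change.** - **Section 5.i item c and Appendix 1, part F:** add *discharged not improved*, *transferred to another hospital* and *left against advice* to the outcome field. Record withdrawal of consent, with its date, as a study status and not as a clinical outcome.
- **Section 5.j item 6:** define positive as discharge by the treating team with complete or partial recovery. Count every other recorded end state (death, discharge not improved, transfer, leaving against advice) as not positive, so that no category is unassigned. Report in-hospital death separately.
- **Cox paragraph for aim 5:** name the event, and state how transfer, leaving against advice and withdrawal are handled.
- **Sample size text:** state which outcome the 60% and 80% refer to.

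The cost is three answer options on one form field, one status item with a date, and a few revised sentences. Patient management does not change. The positive-outcome rate will be slightly lower, and some patients who were improving when they transferred or left will count as not positive. A sensitivity analysis that excludes them can check how much this matters. Telling partial recovery from no improvement remains a judgement by unblinded staff, so a short definition on the form would help.

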For Specific aims 2 and 3, total daily defined dose (DDD) for each antimicrobial agent received by patients will be calculated following WHO guidelines. The total DDD, number of antibiotics, and Duration of antibiotics used will be compared between the groups by calculating Means/SD/95% confidence intervals. Similarly, appropriateness of antibiotic uses will be tested with cross-tabulation using Chi-square analysis.

For specific aim 4, pre-test probability and post-test probability will be determined by both using standard calculations and using Fagan's Nomogram. Correlations between pre- and post-test probabilities for bacterial, rickettsial, viral vs. other causes will be evaluated.

For specific aim 5, the hazard ratio using the Cox proportional hazard model will be calculated to compare the outcomes between the groups. Since multiple factors, such as comorbidities, severity of illness at baseline, type of infection and host immune status, can influence the outcomes, adjustment for these factors will be considered during the univariate and multivariate outcome analyses. Updated Charlson comorbidity index (Quant et al.) will be calculated and used for comparison between the groups [15]. Similarly, qSOFA will be used to stratify the patients by severity of infection [16].

REDCap (Research Electronic Data Capture) software will be used for questionnaire and database entry. SPSS version 25 (IBM, USA) will be used for statistical analysis.

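### Aim 5: the only comparison of discharge status that the protocol names is alive versus dead, so it cannot register a shift from partial to complete recovery, although all three levels are recorded

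*Protocol*

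**What the plan says.** Section 5.i lists discharge status as a three-level outcome: "complete recovery and discharge vs. partial recovery and discharge vs. death". Part F of the Appendix 1 questionnaire records the same three levels in a row of their own.

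Section 5.j, item 6, opens broadly: "Clinical outcomes will be compared for patients whose treatment is based on clinical diagnosis alone (Group 1") against the group with added microbiological diagnosis. It then names one contrast: "Composite Positive outcome (complete or partial recovery) and Negative outcome (in-hospital death) will be compared between the two groups". Part F repeats this cut in a second row, with complete and partial recovery together as the good outcome and "Poor outcome (Death") as the other.

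Further on, section 5.j adds a model: "For specific aim 5, the hazard ratio using the Cox proportional hazard model will be calculated to compare the outcomes between the groups". It does not say what the event is.

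The sample-size section plans aim 5 on "an improvement in clinical outcome for patients whose treatment is based on microbiological diagnosis by 20%, from 60% to 80"%, and concludes: "80% power, the required sample size would be 79 in each arm". It does not say which outcome those percentages measure.

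**The concern.** The recorded outcome has a natural order: complete recovery, partial recovery, death. Pooling the first two levels leaves a two-by-two table of survivors and deaths. If the added tests help survivors to leave hospital fully rather than partly recovered, that table has the same expected counts in both arms, and the comparison can reject only at its error rate.

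Aim 5 could then be reported as showing no difference in outcome while the trial's own database holds the evidence of one. The choice is written into both the analysis section and the form, so it is not a detail left for a later document.

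**Working it through.** **Inputs from the protocol.** 60% to 80% improvement, 80% power and 79 per arm for aim 5; 97 per arm as the minimum and 117 per arm as planned (sample-size section); significance level 0.05 (section 5.j), taken as two-sided because no side is stated; chi-square test for proportions (section 5.j).

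**Inputs assumed.** All splits of complete/partial/death. The protocol gives none, nor any mortality rate.

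**Step 1: the protocol's own figure.** Two proportions, unpooled variance:

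n = (1.96 + 0.8416)² × (0.6×0.4 + 0.8×0.2) / 0.2² = 7.849 × 0.40 / 0.04 = 78.5, rounded up to 79.

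The stated 79 reproduces.

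**Step 2: what 60% to 80% means under the named composite.** If the positive outcome is leaving hospital alive, the negative one is 100% − 60% = 40% in one arm and 100% − 80% = 20% in the other. The planning figure fits the composite only if in-hospital mortality falls from 40% to 20%.

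**Step 3: a gain in complete recovery with equal mortality.** For complete versus not complete, 60% v 80%, the pooled proportion is 0.7 and

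power = Φ[(0.2 − 1.96·√(2×0.7×0.3/n)) / √((0.24 + 0.16)/n)].

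- n = 97: (0.2 − 1.96×0.0658)/0.0642 = 1.106, power 87%.
- n = 117: (0.2 − 1.96×0.0599)/0.0585 = 1.412, power 92%.

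The alive-dead table has no difference to find. Simulation of all three levels (uncorrected chi-square for the two-level cuts, Mann-Whitney for the ordered test) gives these rejection rates:

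| Complete/partial/death, % | Per arm | Alive-dead | Ordered, three levels | Complete v not |
|---|---|---|---|---|
| 60/35/5 v 80/15/5 | 97 | 4-5% | 82% | 87% |
| 60/35/5 v 80/15/5 | 117 | 4-5% | 89% | 92% |

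With equal mortality of 2% to 10%, the ordered test ranges from about 78% to 85% at 97 per arm and from 85% to 91% at 117. Alive-dead stays at about 4-6%.

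**Step 4: some benefit on death as well.** At 117 per arm, 60/35/5 v 80/17/3 gives alive-dead about 10-11% and ordered 91%. For 60/30/10 v 80/15/5 the figures are about 32% and 92%. Halving mortality from 10% to 5% would need about 435 per arm for 80% power on alive-dead.

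**Step 5: cases less favourable to a change.**
- Smaller gain, 60/35/5 v 70/25/5: the ordered test has about 28% at 97 per arm and 32% at 117.
- Benefit mainly on death, 30/30/40 v 40/40/20: alive-dead has 87% and 92%, the ordered test about 73% and 81%. This is also the case in which survival goes from 60% to 80%.

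**The case against.** A reader might infer that aim 5 cannot detect any gain in recovery, or that death is the only outcome it will examine. The text does not support that. Item 6 opens with clinical outcomes in general, time to defervescence and antimicrobial de-escalation are also recorded, the Cox model has no stated event, and the form keeps the three-level row beside the composite. Any of these leaves room for another analysis, and a statistical analysis plan that is not shown may name one. What stands is narrower: among contrasts of discharge status, alive versus dead is the only one named.

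A reader might also take a shift from partial to complete recovery to be the likeliest effect of better diagnosis. The protocol does not say so; its hypothesis concerns the use of broad-spectrum antimicrobials.

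Three further objections carry weight. In-hospital death is objective, whereas complete and partial recovery are undefined and judged in an open-label trial, so added power could come with assessment bias. The ordered test is not better in every case: alive-dead wins when the benefit is on death, and a plain complete-versus-not comparison does slightly better when mortality is equal. And with a 10-point gain the ordered test would still usually miss the effect. These points limit the claim and shape the remedy. They do not alter the fact that the named composite ignores a distinction the trial records.

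**Conclusion.** The point holds in this limited form. The named composite for aim 5 has no power for a shift from partial to complete recovery. Under an assumed 60% v 80% complete recovery with 5% mortality in both arms, it rejects at about its error rate (4-5%), against 82-89% for an ordered test and 87-92% for complete versus not complete, at 97 to 117 per arm.

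The size depends on assumed splits. The advantage shrinks to about 28-32% against 4-5% when the gain is 10 points, and it reverses when the benefit is mainly on death. The open meaning of 60% to 80% matters here: read as survival, it implies mortality of 40% v 20%, for which no support is given; read as complete recovery, it is a gain that the named comparison cannot register. Aim 5 is secondary, so this is an improvement that should be made, not a threat to the primary aims.

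**What to change.** 1. In section 5.j, item 6, compare the recorded three-level outcome between arms with an ordered test or a proportional odds model. Report the percentage in each level by arm, with risk differences.
2. Keep in-hospital death as a separately reported component, so that an effect on mortality stays visible.
3. Align the Cox sentence in section 5.j (name its event, or remove it for this outcome) and the composite row in part F of the questionnaire.
4. In the sample-size section, state which outcome the 60% to 80% refers to.
5. Put one fixed definition of complete recovery on the form before enrolment, applied in the same way in both arms.

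The cost is a few sentences in section 5.j and the sample-size section, plus an edit to the form. No extra patients, visits or variables are needed. The downside is that an open-label judgement of recovery then carries more of aim 5; the fixed definition and the separate report of death reduce that risk without removing it.
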